AIM2	From the qualitative arm, we plan to adapt the program for use with college men in Vietnam and to test whether it: H1 improves their knowledge, attitudes, and emotional valence regarding sexual violence against women H2 increases their tendency to intervene to prevent such violence; and H3 reduces their propensity to perpetrate sexual violence against women.

Qualitative Study Design

Organizational structure of the team	Translation, Recruitment, Training, and Ethics/Research Committee Approval. Contributions to Data Collection, Analyses, Interpretation, Writing, and Dissemination Activities.
---	---

	
CCIHP Site Principal Investigator: [name], MSc Research Assistants (Total = 2) for Pilot, SSIs, FGDs Interviewers: (4, ≥ Master’s level) Supervisor: (1, ≥ Master’s level)
 
Emory University IRB Approval, Contributions to Data Collection, Analyses, Interpretation, Writing, and Dissemination Activities. Emory University Principal Investigator: [name] Co-Investigator: [name] Consultant: [name]

Setting and location
	
Setting. The undergraduate system in Vietnam is a suitable context for adapting the program, given its similarities with the US context where the program originated. Undergraduate study is 4–6 years, with two foundational years and 2–4 years for specialization. Except for political education and national defense, universities design their own curricular and extra-curricular activities and maintain networks through the Ministry of Education and Training (MoET), professional associations, and Youth Union, all potential pathways to bring the program to scale in the future.
 
Study site. The sites for this project are Hanoi Medical University (HMU) and Thang Long University (TLU), both in Hanoi. HMU is a 100-year-old state school with dental, medical, nursing, nutrition, public health, and paramedical/ ophthalmology technical programs. Its 1000 enrolled students are 40% men. TLU is a 24-year-old private university with 15 departments (e.g., math, business administration, social sciences). Its 7000 enrolled students are 45%-50% men. Both schools have provided letters of support for adaptation of the program with their students.

Study Population
	
In step 1 of the qualitative work, we will conduct semi-structured interviews (SSIs) with undergraduate men and women and meetings with university stakeholders. In step 2, we will conduct FGDs with college men..

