Bystander self-efficacy	ROLB self-efficacy to intervene in SV ¹⁰¹	When I hear a sexist comment I indicate displeasure	8	1-7
Bystander intervention	ROLB self-behavior subscale ¹⁰¹	walk into my room & roommates are watching porn	5	1-7
Intimate Partner Violence	Revised Conflict Tactics Scale (CTS2) SV ¹⁰²	Used force to make partner have sex	7	1-6
Sexual Violence	Sexual Experiences Survey Rev. (SES-R), SV ¹⁰³	put my penis, fingers, objects into so's butt w/o...consent	8	0-3
Secondary Outcomes (Knowledge, Attitudinal, Emotional Mediators)				
Knowledge of law	Knowledge of legal defs of assault/rape scale ¹⁰⁴	Sex intercourse w/so <16 [is legal if] he/she gives consent	9	T/F
Knowledge of consent	Knowledge of informed consent to have sex ⁶⁸	If a woman dsn't physically resist sex, she has given consent	14	T/F
Norms degrading wn	ROLB other-behavior subscale ¹⁰¹	Rmate suggests...give alcohol to your date to 'loosen her up'	5	1-7
Gender attitudes	Hostility Toward Women Scale ^{105,106}	...many times women flirt w/men just to tease/hurt them	10	T/F
Gender attitudes	Hyper-Gender Ideology Scale short form (HGIS) ¹⁰⁷	If men pay for a date, they deserve smthg in return	19	1-5
Rape attitudes	College Data Rape Attitude & Behavior Survey ¹⁰⁸	...sex jokes and innuendos are only fun & harmless	20	1-5
Rape attitudes	Illinois Rape Myth Acceptance (IRMA) ⁴⁸	Rape happens when a man's sex drive gets out of ctrl	17	1-5
Dating violence attitudes	Attitudes Toward Male Dating Violence Scale ¹⁰⁹	A guy should not insult his girlfriend	39	1-5
Empathy for rape victims	Rape Empathy Scale (RES) ⁵⁴	In general,...rape is not...provoked by the rape victim	19	1-5
Control Variables				
Alcohol use	National College Health Assessment Survey ¹¹⁰	# drinks consumed when last partied	1	#
Sexual behavior	Safe Sex Behavior Questionnaire (SSBQ) ¹¹¹	engage in sex intercourse on the first date	7	1-4
Sexual communication	Communication self-efficacy ¹¹² (to discuss sex)	can discuss...using condoms w/any sex partner	4	1-10
total items and time required			192	42 m

Note. SV = sexual violence; α indicates the reliability of the scale in other samples.

Informed Consent

Assurances, IRB approvals, and oversight: Our ethics protocol will follow WHO guidelines for research on violence against women.¹³¹ Ethical approval will be sought from CCIHP, Emory University, and Georgia State University. Team members have completed certification training in research ethics.

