We then will assess the impact of the program on our main outcomes (H2, H3). With reference to Figure 2, each of these relationships is captured by the product of the two paths, ab , or the indirect or mediating impact of the program on our primary outcomes, transmitted through the individual mediators. Testing the significance of each product allows us to assess the significance of each path. To test these mediated effects, we will use confidence intervals derived from the bias-corrected percentile-based bootstrap approach, a resampling technique, as the valid use of regular standard errors relies on the unrealistic normality assumption, given that the products of two normally distributed regression coefficients is not normally distributed in general.^{117,118} A consequence is that the power of the test is reduced.¹¹⁷ The bootstrap approach is suitable here, as it allows researchers to assess the test statistics associated with these mediated effects without knowledge of their true distributions.⁸⁹ The standardized indirect effect coefficients with confidence intervals will serve as effect size measures of the various mediation effects.

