We will test the robustness of the results obtained by investigating potential confounders of paths a and b, which may result in biased estimates. Figure 3 shows how confounders may affect the estimates of relationships between 1) treatment and mediator with tm_1 and tm_2 , and 2) mediator and outcome with mo_1 and mo_2 , which may be biased as a result of omitted or confounding variables.^{117,119} As there will be randomization of the program treatment but not of the mediator variables, most confounders on the treatment-to-mediator relation should be eliminated. Still, we will, perform a balance check on randomization using the control variables listed in Table 5. If imbalance on certain variables is detected, those variables may be controlled for when estimating path a, the program treatment-to-mediator relation. We also will assess the sensitivity of the results to the potential confounders on the mediator-to-outcome relation, path b, using a propensity score approach.^{120,121} The propensity score, or the probability that an individual receives a specified level of the mediator, given a set of observed covariates chosen from Table 5, will be estimated and used as a covariate in the mediation model to estimate path b. The results will be compared to those without any adjustment to detect if possible biases exist due to omitted observed confounders, and if they do, what the directions and magnitude are.

We will perform the intent-to-treat analyses using the software program, Mplus.⁹⁶

Supplemental analyses in the program group. We will conduct several analyses in the program group to assist with the interpretation of findings from the intent-to-treat analyses. First, to gauge possible dose-response relationships between engagement with the program, such as total contact time over the six-session program, and individual post-treatment mediator and outcome variables, we will examine their partial correlations for participants assigned to the program group, adjusting for their corresponding baseline values.¹²² Second, we will assess differential program impact by examining differences in pretest-posttest change scores in mediator and outcome variables across socio-demographic characteristics, such as age, and risk groups, such as alcohol use.

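### H2 is judged by indirect effects with no check for unmeasured mediator–outcome correlation, a risk plausibly greatest where the norms mediator and both bystander outcomes are ROLB scales

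*Combined protocol and SAP*

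**What the plan says.** Under Quantitative Study Design, Table 2 lists two bystander primary outcomes: the "ROLB self-efficacy to intervene in SV" (8 items) and the "ROLB self-behavior subscale" (5 items). Under the heading "Secondary Outcomes (Knowledge, Attitudinal, Emotional Mediators" it lists norms degrading women, measured by the "ROLB other-behavior subscale" (5 items). All three carry reference 101 and a 1–7 response scale. No other mediator in Table 2 shares a named instrument with a primary outcome.

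The Goals/Aims section states "H2 increases their tendency to intervene to prevent such violence". In Plans for analysis, Intent-to-treat analysis, the program's impact on the outcomes of H2 and H3 is defined through mediation: "each of these relationships is captured by the product of the two paths". Inference uses bias-corrected bootstrap intervals, one mediator at a time, and the text adds: "Testing the significance of each product allows us to assess the significance of each path".

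The robustness paragraph acknowledges that the mediators are not randomised. Its check on path b is a propensity score built from observed covariates and entered in the model, "to detect if possible biases exist due to omitted observed confounders".

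**The concern.** Randomisation protects path a and the total effect of assignment on each outcome. It does not protect path b. Two scales answered by the same man in the same online survey can correlate because of response style, similar wording, or a habit of assuming that peers act as he does. If the program then shifts the mediator, that correlation alone gives a non-zero ab. A propensity score removes only what its covariates capture, and response style is not captured unless it is measured and entered.

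The written analysis sets out no test of the total randomised effect as the basis for H2. A significant ab could therefore be read as increased bystander behaviour in a trial whose arms do not differ on bystander behaviour.

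**Working it through.** **Inputs from the documents.** Planned sample 400, allocated 1:1, with 30% attrition: 400 × 0.70 = 280 completers. The power statement gives no alpha, no numerical a and b, and no number of mediators. The figure of 400 can be neither reproduced nor called wrong, and this point does not depend on it. The item counts in Table 2 sum to the stated 192 with the three ROLB scales counted separately as 8 + 5 + 5, so no shared items are shown.

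**Assumptions, not in the documents.** Two-sided 5% level; program effect on the mediator d = 0.3 or 0.4; residual mediator–outcome correlation r = 0 to 0.3; mediator and outcome at one wave, without baseline scores.

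**Null model.** With T = 0 or 1, let M = dT + e1 and Y = e2, with unit variances and corr(e1, e2) = r. There is no causal path b and no total effect. Regressing Y on M and T gives an expected b of r and an expected direct effect of −d·r. The estimated product centres on d·r (for example 0.4 × 0.2 = 0.08), and the two pieces cancel to the true total of zero.

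**Hand approximation.** Treat ab as significant when both paths are. Then Za = d√280/2 and Zb = r√280/√(1 − r²).

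- d = 0.4: Za = 3.35, so path a is significant with probability 0.92. d = 0.3: Za = 2.51, probability 0.71.
- r = 0.1, 0.2, 0.3: Zb = 1.68, 3.42, 5.26, with probabilities 0.39, 0.93, 1.00.
- Products at d = 0.4: 0.36, 0.85, 0.92. At d = 0.3: 0.28, 0.66, 0.71.

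The rate is capped by the power for path a. At 280 completers a partial correlation of 0.117 is already significant at 5%.

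**Simulation of the same null model.** Share of trials in which the interval for ab excludes zero, as ranges over repeated runs (600 or 1,000 trials each where recorded):

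| d | r | Percentile interval | Bias-corrected interval (the plan's method) |
|---|---|---|---|
| 0.4 | 0.1 | 34–36% | 44–52% |
| 0.4 | 0.2 | 82–85% | 89–90% |
| 0.4 | 0.3 | 91–94% | 92–96% |
| 0.3 | 0.1 | 25–29% | 37–39% |
| 0.3 | 0.2 | 60–65% | 70–74% |
| 0.3 | 0.3 | 71–73% | 76% |

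**A second parameterisation.** Here a common method factor carries a share w of each scale's residual variance, with bias-corrected intervals.

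| R² of path a | w = 0 | 0.05 | 0.10 | 0.20 | 0.30 |
|---|---|---|---|---|---|
| 0.13 (the plan's lower value) | 8% | 16% | 41% | 93% | 100% |
| 0.02 | 6% | 16% | 35% | 68% | 71% |

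With path a = 0 the rate is 1–9% across the same shares, so the artefact needs the program to move the mediator. H1 predicts that it will.

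**Comparator.** In the same null trials, the test of the randomised total effect is significant in 3–8%.

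**Does the proposed check work?** Let r_obs be the partial correlation of M and Y given T, and s_M, s_Y the residual SDs given T. Fixing the residual correlation at ρ, with the direct path kept in the model, gives b(ρ) = (s_Y/s_M)·[r_obs − ρ√((1 − r_obs²)/(1 − ρ²))]. This is zero at ρ = r_obs. Fixing ρ at its true value brought the false-positive rate to about 4–6% in one run and 6–9% in a second of 1,000 trials. The bias-corrected interval already runs at 6–8% in the w = 0 column above, so this is close to its own baseline.

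**The case against.** Several parts of the opposing case stand.

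- **Not specific to ROLB.** Every mediator and outcome is self-reported by the same man, so unmeasured correlation threatens every product. The ROLB pairs are only the case where it is easiest to expect.
- **Size is not anchored.** The documents give no inter-scale correlations. At r = 0.05 the simulated percentile rate is only about 9% (d = 0.3) to 13% (d = 0.4).
- **Common instrument is inferred.** A reader might infer that the three scales are overlapping parts of one questionnaire. Table 2 shows a shared label, citation and format. It does not call self-efficacy a subscale, so that link is the weakest, and it shows no item overlap.
- **No one-product rule.** A reader might infer that one significant product is enough to declare H2 met. The plan does not say so. It states no rule either way.
- **Partial protections exist.** Field Methods names social desirability among the confounders to be considered, and the descriptive analyses include psychometric assessment. Taking the mediator at posttest and the outcome at six months, with baseline adjustment, would also help. But social desirability has no row in Table 2, the psychometric sentence sets no rule for shared-method variance, and the text on the path model specifies neither wave nor baseline adjustment. Figures 2 and 3 are not available here and might show more.
- **Association may be real.** The Background rests on learning by observing others, so norms and behaviour should correlate. This is also the only norms mediator. Barring the ROLB products from H2 would remove the whole norms pathway, and the documents do not justify that.

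**Conclusion.** The concern holds in limited form. H2 is assessed through ab, path b is open to unmeasured mediator–outcome correlation, and the stated propensity adjustment cannot reach what its covariates do not measure. With no mediation and no total effect, ab would exclude zero in roughly 30–95% of trials at 280 completers, taking the hand approximation and the bias-corrected runs together. That range rests on assumed d = 0.3–0.4 and r = 0.1–0.3, on one wave, and on no baseline adjustment. The true figure for this trial is unknown and could be much lower.

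The documents do not support saying that a false H2 result will occur, that the ROLB products are invalid, or that the randomised comparison is compromised. What is missing is a stated way of showing how much unmeasured correlation each mediation result can withstand.

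**What to change.** In Plans for analysis, after the propensity-score paragraph, add:

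1. For every product used for H2 or H3, refit the path model, including the direct treatment-to-outcome path, with the mediator–outcome residual correlation fixed at 0.1, 0.2 and 0.3 in both signs. Report the value at which the interval for ab comes to include zero.
2. Flag the products of ROLB other-behavior with ROLB self-behavior and with ROLB self-efficacy as sharing an instrument label, and keep them in the analysis. Do not rest H2 on them alone if they fail at small values of the residual correlation.
3. Report the randomised total effect on each bystander outcome, with its confidence interval, beside ab.

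The cost is SAP wording and extra Mplus runs, with no new data. There are 3 × 2 = 6 refits per product. If all nine mediator scales and four primary outcomes in Table 2 are paired, that is 9 × 4 × 6 = 216 refits, which can be scripted. With the seven mediators named in the study design paragraph it is 7 × 4 × 6 = 168. The other cost is a possibly more cautious mediation claim.

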
Data Management and monitoring
	
Data systems will be designed to handle the concurrent collection, processing, secure storage, and analysis of project data. New data will be aggregated progressively via a web-based data-entry application (REDCap). Each participant will be assigned a unique number identifying him across waves. The web application will transmit data entered by each participant through an encrypted network connection to a centralized database running on a secure network and infrastructure, ensuring secure electronic data movement. A CCIHP programmer will create, and a CCIHP data manager will run, applications for more refined range/ consistency checks in the centralized database. Systematic data collection errors can be identified, resolved, and documented using a workflow module of the REDCap application. Some statistical software can access data in the central database and store derived variables there. For analyses done with external statistical software, de-identified data will be extracted and held on HIPAA compliant secure networks and computing workstations.

Plans for analysis

[figure not shown]

Descriptive analyses. We will perform univariate analysis of all demographic, screening, mediating, outcome, and control variables for the program and the health-education control groups, individually and combined, to explore distributions, outliers, and missingness. The associations between individual pairs of variables will be examined. Baseline differences on these variables between the program and health-education control condition will be tested. The psychometric properties of the various instruments will be assessed and confirmed.

Intent-to-treat analysis. To assess our aims based on the randomization scheme,¹¹⁴ we will perform mediation analyses via path analysis.^{115,116} Namely, we will assess first whether, relative to men randomized to the health-education control group, men randomized to the program will have improved mediating outcomes (H1). With reference to Figure 2, each of these relationships is represented by path a, or the direct effect of treatment on the mediator. Testing the significance of each path allows us to assess the impact of the program on each mediator. The standardized effect coefficients will serve as effect size measures of the treatment to mediator relations.

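### H2 and H3 are decided by the indirect effect ab, and no text states a post-baseline comparison of the primary outcomes by randomised arm

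*Combined protocol and SAP*

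**What the plan says.** - **Hypotheses.** Goals/Aims, AIM2, asks whether the program "increases their tendency to intervene to prevent such violence; and H3 reduces their propensity to perpetrate sexual violence against women". These are effects of the program on behaviour.
- **Decision rule.** Plans for analysis, Intent-to-treat analysis, opens with "we will perform mediation analyses via path analysis". H1 gets an arm comparison, path a, for each mediator. For the main outcomes (H2, H3), "each of these relationships is captured by the product of the two paths", ab, and "Testing the significance of each product allows us to assess the significance of each path". The test is a bias-corrected bootstrap interval.
- **Descriptive analyses.** Variables are summarised "for the program and the health-education control groups, individually and combined, to explore distributions, outliers, and missingness". The only arm difference said to be tested is at baseline: "Baseline differences on these variables between the program and health-education control condition will be tested".
- **Supplemental analyses.** The change scores are within the program group only.
- **Analytic issues and strategies.** Outcome estimates are compared before and after reweighting. A CACE analysis serves as a robustness check.
- **Path b.** The robustness paragraph contrasts the two paths: "As there will be randomization of the program treatment but not of the mediator variables". It plans a propensity-score sensitivity check of path b, "given a set of observed covariates chosen from Table 5".

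**The concern.** Randomisation protects the comparison of arms. It protects path a, but not path b, which is an observed association between a mediator and behaviour. Attitudes to sexual violence and self-reported behaviour may well be correlated before any intervention. If the program moves the attitude and leaves behaviour alone, that existing correlation enters b and makes ab non-zero. The plan would then report more bystanding or less perpetration although the two arms behave the same. Conversely, a real effect on behaviour that bypasses the measured mediators does not appear in ab. Both errors concern the trial's headline conclusions.

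**Working it through.** **1. The plan's own figure.** Survey sample and power gives power .80, R² of .13 and .26, 30% attrition and 400 men. So 400 × 0.7 = 280 completers, or 140 per arm. The values of a and b, the alpha, the number of mediators and the required N are not printed, so the Mplus run cannot be rebuilt. In a single-mediator simulation (arm coded -1/+1, unit residuals), ab reaches 80% power at about 65-75 completers for R² = .13, and power is about 100% at 280. The figure is therefore not recovered, and it does not bear on this point either way.

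**2. Why ab can be non-zero with no effect on behaviour.** Assume a mediator with within-arm SD 1 shifted by 0.5 SD, an outcome with SD 1 that is not shifted, and a within-arm correlation r. Regressing outcome on arm and mediator gives b = r and a direct effect of -0.5r. At r = .3, ab = 0.5 × .3 = .15, the direct effect is -.15 and the total effect is 0.

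Hand check at n = 280:
- a/SE = 0.5/(2/√280) = 4.18, significant in about 99% of trials.
- b/SE = r/√((1 - r²)/280), which is 1.68 at r = .1 (significant in about 39%) and 5.26 at r = .3 (nearly always).
- Both paths significant: about 5% at r = 0, 39% at .1 and 99% at .3.

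**3. Simulation with the planned type of interval.** Assumed: 95% bias-corrected bootstrap (the plan states no level) and retest correlation q = .7 unless noted. M_t = √q·T_M + √(1-q)·e, and likewise for Y. corr(T_M, T_Y) = r/q, so the observed correlation is r. The mediator gains 0.5 in the program arm and the outcome gains nothing. Simulation error is up to about 3 percentage points.

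| Model for ab | r | ab rejects |
|---|---|---|
| No baseline adjustment | 0 | 7-9% |
| No baseline adjustment | .1 | 40-46% |
| No baseline adjustment | .3 | 98-99% |
| Baseline mediator and outcome adjusted | .3 | about 20% |
| Same, retest .85 | .3 | about 8-12% |

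The arm comparison rejects in about 5% throughout.

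**4. Opposing direct effect.** With a = b = .387 (arm coded -1/+1) and a direct effect of -ab, ab is significant in 100% of trials and the arm comparison in about 6%.

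**5. Reverse error.** If the outcome shifts 0.4 SD outside the mediator, ab rejects in under about 10% and the arm comparison in about 90%.

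**6. Power of the arm comparison.** Two-sided t test, 140 per arm. Adjusting for a baseline correlation ρ divides the standardised difference d by √(1 - ρ²).
- Detectable d at 80% power: 0.34, or 0.34 × √(1 - .49) = 0.24 with an assumed ρ = .7. At alpha .05/4 = .0125: 0.40 and 0.29.
- Full mediation, arm coded -1/+1, unit residuals: d = 2ab/√(1 + b²). At R² = .13, a = b = √.13 = .361 gives .26/√1.13 = .245 and power 53%. Taking a = b = √(.13/.87) = .387 gives .279 and power 64%. Fully standardised paths give 2(.13)/√(1 - .13²) = .262 and 59%. The first reading is slightly low, since its mediator R² is .13/1.13 = .115.
- With ρ = .7 the R² = .13 range becomes 82-90%. At alpha .0125, unadjusted, it is 32-43%.
- At R² = .26 (d = .463 to .604), power at alpha .05 is 97% or more.

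**The case against.** **Mediation is a stated aim.** The Introduction and the Study design paragraph both describe change in behaviour through the mediators, so ab belongs in the plan. That stands. It does not make ab a test of H2 and H3 as AIM2 words them, and those sections need reconciling.

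**The plan may contain a direct path.** Figure 2 is not shown and may draw one. A reader might infer that the model omits the direct effect altogether; the documents do not support that. What can be said is that no text uses a direct or total effect to decide H2 or H3.

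**CACE.** A reader might infer that no arm contrast on behaviour is planned anywhere. That goes too far: CACE is an arm contrast among compliers. But it is a robustness check and names no outcome, time point or test.

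**Confounding is recognised.** The propensity check is planned, Field Methods names candidate confounders, and Table 2 lists control variables. Table 5 is not in the text available, which is not counted against the plan. The check remains a sensitivity analysis on observed covariates.

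**Attitude change alone.** A reader might infer that any shift in attitudes would yield a false claim about behaviour. It would not: with mediator and outcome unrelated and no opposing direct effect, ab rejects in only about 7-9%. Confounding or an opposing direct effect is needed.

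**Conclusion.** The point holds. As written, H2 and H3 are concluded from a quantity that rests on an unrandomised path, and the text gives no by-arm test of the primary outcomes that would expose a wrong conclusion. The size of the error depends on inputs the documents do not give: the mediator-outcome correlation, the retest correlation, the mediator shift and whether baseline values are adjusted. It ranges from close to nominal to near-certain rejection without adjustment, and adjustment reduces it substantially without removing it in the cases run. The simulations assume one mediator and continuous normal outcomes.

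A reader might also infer that the arm comparison would have very low power by placing a = b = .387 on a 0/1 arm. That implies a mediator R² of .25 × .387²/(1 + .25 × .387²) = .036, not the stated .13, so it is not the planned effect.

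**What to change.** 1. Make the comparison of each primary outcome by randomised arm the test of H2 and H3, at a named follow-up, adjusted for the outcome's baseline value, with a multiplicity rule for the four outcomes.
2. Keep ab as the mediation analysis for the aim in the Introduction and Study design. Include baseline mediator and baseline outcome as covariates, and report ab beside the total and direct effects. Do not claim H2 or H3 from ab alone.
3. Restate Survey sample and power for the arm comparison, with enrolment unchanged.

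The cost is revised wording, one regression per primary outcome on data already being collected, and a rewritten power paragraph. The downside is real: positive claims become harder, and at R² = .13 the unadjusted arm comparison falls short of .80. Baseline adjustment recovers this at alpha .05 if the baseline correlation is near .7.

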Survey sample and power. Men 18–24 years and identifying as heterosexual or bisexual and enrolled at HMU and TLU as freshmen on 9/1/2019 are eligible. According to recent enrollment figures, about 890 men matriculate yearly at HMU and TLU. Given a cooperation rate of 67% in similarly focused research among male Atlanta-based undergraduates,⁶⁸ this pool is sufficient to recruit a sample of 400 freshman men for participation in this study.

We computed the required sample sizes to detect our hypothesized effects with a power of .80. We used a Monte Carlo approach⁹¹ to calculate the required sample sizes 1) assuming an attrition rate of 30%; based on 2) Cohen’s medium-to-large-effect-categorization⁹² with regards to the proportion of the variance accounted for, R², by the model (.13 and .26) using corresponding values for a and b;⁹³⁻⁹⁵ and 2) a desired power level of .80. The computer program, Mplus,⁹⁶ was used to complete the computations.

To recruit students, CCIHP personnel will contact department chairs at each university to discuss the study with them. With their agreement, CCIHP will talk with faculty about the study and ask them to announce it in their classes using a flyer with a brief, standard project description. The department chair will obtain email and phone numbers of students. The team has used this strategy successfully to recruit undergraduates. The study staff will utilize student phone numbers to contact students to make sure they check their emails.

Field Methods

Data collection overview. After consent, participants will be assigned randomly, with an equal allocation to Real-Consent or a health-education

control program, using block randomization with random block sizes. Participants and analysts will be blinded to assignments.

Outcomes will be assessed at baseline, posttest (just after finishing the last module), and six months (Table 2). We will consider confounders and modifiers, like social desirability, emotional adjustment, sensation seeking, sexual behavior, aggressive peers, peer and social network diversity, peer social support, witnessing family violence, family cohesion, and social support (Table 2). Questions will model others in the field.⁶⁸

Table 2. Primary (Behavioral) and Secondary (Knowledge/Attitudinal/Emotional) Outcomes at Baseline, Posttest, and Six-Month Follow-Up				
Construct	Scale	Sample item	#	Resp
Primary Outcomes				

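### H2 and H3 rest on bias-corrected bootstrap intervals, which run above an assumed 5% level when the program clearly moves a mediator that has no effect on behaviour

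*Combined protocol and SAP*

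**What the plan says.** In the quantitative Plans for analysis, under Intent-to-treat analysis, H1 is tested by path a, the program's effect on each mediator. For H2 and H3, "each of these relationships is captured by the product of the two paths", and to test those products "we will use confidence intervals derived from the bias-corrected percentile-based bootstrap approach, a resampling technique". The natural reading is that a mediated effect is declared when the interval for ab excludes zero. The stated reason is that a product of two coefficients is not normally distributed. The section does not discuss false-positive error.

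The same intervals serve as estimates: "The standardized indirect effect coefficients with confidence intervals will serve as effect size measures of the various mediation effects". No alpha, confidence level, sidedness or number of bootstrap draws is given.

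Table 2 lists two perpetration scales among the primary outcomes, "Sexual Experiences Survey Rev. (SES-R), SV" and the CTS2 sexual violence scale. The plan does not say how scores with many zeros will be modelled.

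**The concern.** The null that matters most here is that attitudes or knowledge improve but behaviour does not follow: a is non-zero and b is zero. The bias correction is weakest in that case. The bootstrap distribution of ab is skewed in the direction of its own sign, so its median lies nearer zero than the estimate does. The correction responds by moving both limits away from zero, and the interval then excludes zero more often than its nominal level allows.

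At stake is a claim that the program changed bystander behaviour or reduced perpetration, made on a test whose error rate can exceed the level a reader would assume. This concerns the level of each single test and is separate from the number of products tested.

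**Working it through.** **Inputs from the plan.** Enrolment is 400 ("recruit a sample of 400 freshman men for participation in this study"), allocation is 1:1 and attrition is 30%, so 400 × 0.70 = 280 are analysed. The power statement is "We computed the required sample sizes to detect our hypothesized effects with a power of .80", with effects given as R² "by the model (.13 and .26) using corresponding values for a and b". The numerical a and b are not reported.

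**The plan's own figure.** 400 cannot be reproduced as the number needed for power .80. If standardized a = b = .39 is assumed, bias-corrected power reaches .80 at about 60 analysed, and 60 / 0.70 = 86 enrolled. If .39 is read as the effect of a 0/1 treatment code, with b = .39, power at 280 is .92. The sample is adequate under either reading. The issue here is the error rate.

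**Assumptions.** Two-sided 95% intervals, 1,000 draws, one mediator, linear model, no covariates. M = aX + e; Y is regressed on M and X; the true b is 0.

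**Formulas.**
- z0 = Φ⁻¹(share of resampled ab below the estimate).
- Bias-corrected limits: the resampled percentiles at Φ(2·z0 ± 1.96).
- Plain percentile limits: the same with z0 = 0.
- Joint significance: a and b each significant at 5%.
- Conversion: standardized a = (d/2)/√(1 + (d/2)²). For example, d = 0.5 gives 0.25/√1.0625 = .243.

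**Roughly continuous outcome, n = 280, false-positive rate (%).**

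| Standardized a | d (approx.) | Bias-corrected | Percentile | Joint |
|---|---|---|---|---|
| 0 | 0 | 0.5 | | |
| .10 | 0.20 | 3.2 | | |
| .14 | 0.28 | 5.5 | | |
| .19 | 0.39 | 7.6 | 4.5 | 4.5 |
| .24 | 0.50 | 7.6 | 5.3 | 4.9 |
| .28 | 0.59 | 7.2 | 5.5 | 5.0 |
| .36 (√.13) | 0.77 | 6.6 | 5.6 | 5.0 |
| .51 (√.26) | 1.19 | 5.9 | 5.6 | 5.0 |

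The rows from .19 down use 20,000 data sets each, with a Monte Carlo standard error near √(.076 × .924/20000) = 0.2 points. Separate simulations with 1,200 to 4,000 data sets gave 6.2-7.7% at d = 0.4 and 7.7-7.9% at d = 0.5. With 5,000 draws the rate at a = .20 is 7.3%, so too few draws is not the cause. With all 400 men the peak is 7.6% in one run and 8.2% in another.

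**Sparse perpetration score, linear model, n = 280 (%).** The documents give no perpetration rate for this population, so a range is shown. The Background section reports 0.2% for men's sexual violence perpetration and 12.0% for women's victimization. Analytic issues and strategies reports 37% for men's partner violence perpetration. The other rates are assumed, as is the skewed shape of the non-zero scores.

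| Men with non-zero score | Expected of 280 | Bias-corrected | Percentile | Joint |
|---|---|---|---|---|
| 0.2% | 0.6 | 0.2-0.3 | 0.0 | 1.6-2.3 |
| 2% | 5.6 | 11.5-13.5 | 6.1-7.4 | 4.6-5.2 |
| 5% | 14 | 11.3-12.9 | 6.7-8.0 | 4.4-5.0 |
| 10% | 28 | 9.3-11.2 | 6.1-7.3 | 4.6-5.1 |
| 12% | 33.6 | 9.0-10.7 | 5.9-7.0 | 4.5-5.2 |
| 37% | 103.6 | 7.0-8.4 | 4.9-5.9 | 4.4-4.9 |

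Ranges are over standardized a of .19 to .51 (.14 to .39 in the 0.2% row). At 3%, with a of .14 to .39, the bias-corrected rate was 12.7-15.8% and the percentile rate 5.3-10.0%. A binary perpetration outcome gave 10-13% at 2-3%, 9-11% at 5% and 6-8% at 10-37%.

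**The case against.** The plan's reason for bootstrapping a product is sound, and for continuous outcomes the excess is only about 1 to 3 points. A reader might infer that every H2 and H3 claim carries an inflated error rate. The first table does not support that: the rate is below 5% for a weak mediator effect and falls back towards 6% for a very strong one. A weak effect is limited comfort once H1 has been declared, however. In one simulation at d = 0.2, the rate among data sets with a significant path a was 8.9% (about 440 data sets, standard error about 1.4 points).

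A reader might also infer that perpetration claims run at 11-14%. The documents do not support that as a general figure. It needs a prevalence of a few percent, which they do not give, and it fails at both men's perpetration rates they do give. It also supposes a linear model that the plan does not specify. Nor is the bias correction the whole cause, because the percentile interval is also too liberal in much of the sparse range.

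The plan offers some protection. It inspects distributions, and it compares results with and without values beyond z = ±3. Suppose 5% of men are non-zero, with scores uniform on 1-6. The mean is .05 × 3.5 = .175 and the variance is .05 × 91/6 − .175² = .728, so the cutoff is .175 + 3 × .853 = 2.73. Scores of 3 or more, two-thirds of the non-zero values, would then be dropped. That could expose a result driven by a few men, but it is a sensitivity comparison and does not control the error of the main test.

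**Conclusion.** The concern holds in a conditional form. With 280 completers and an assumed two-sided 5% level, the stated test for H2 and H3 is too liberal when the program clearly moves a mediator that does not affect behaviour. The rate is up to about 7.5-8% for roughly continuous outcomes at d of about 0.4-0.6. At standardized a of .36-.51, one reading of the plan's R² values, it is about 6-6.6%. For sparse perpetration scores the size depends on a prevalence the documents do not settle, and could reach about 11-14% at a few percent.

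It cannot be said that the trial breaches its own alpha, since none is stated. Several mediators at once, covariate or propensity adjustment, weighting and Mplus-specific options were not simulated. Joint significance stayed near or below 5% in every setting where it was computed. Severity: should-fix.

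**What to change.** In Intent-to-treat analysis, replace the bias-corrected interval as the decision rule:

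- State a two-sided alpha of .05 and the number of bootstrap draws (for example 5,000).
- Declare a mediated effect only if path a and path b are each significant at that level.
- Report the plain percentile bootstrap interval for ab as the interval estimate. Say that the joint test decides if the two disagree.
- For SES-R and the CTS2 sexual violence scale, let the joint test decide and state that the interval is descriptive, because the percentile interval can itself run above 5% on sparse scores.

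The cost is SAP wording within the same Mplus path model, plus a small loss of power: about 0.89 to 0.84 at d = 0.4 and b = 0.2 with 280 completers. Part of that loss was inflated error. At d = .39 and b = .39 the change is from .92 to .91. The joint-test error rates above are for a linear model, so they should be rechecked if another model is chosen for the perpetration scores.
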